5.3.3. Sensitivity analyses

No sensitivity analyses are planned for secondary efficacy endpoints.

5.3.4. Supplementary analyses

No supplementary analyses are planned for secondary efficacy endpoints.

5.3.5. Subgroup analyses

No subgroup analyses are planned for secondary efficacy endpoints.

5.4. Safety Analyses

Displays will be based on GSK Core Data Standards. No formal statistical testing will be performed on Safety data.

5.4.1. Extent of Exposure

Descriptive summaries of exposure data will be provided, including the average dose taken, duration of exposure and cumulative actual dose. Study intervention compliance will be reported in exposure listings and will be defined in the OPS.

The following definitions will be used for exposure:

- Duration of exposure (days) is defined as time between first and last dose dates (last dose-first dose +1).
- Cumulative actual dose (mg) is defined as the total actual dose received (mg) during the 12-week treatment period (total number of active tablets taken x 480mg).
- The average daily dose (mg) taken is defined as the cumulative actual dose divided by the duration of exposure.

Cumulative actual dose will be determined from the number of tablets in dispensed and returned bottles.

5.4.2. Adverse Events

Adverse event (AE) analyses including the analysis of AEs, Serious AEs (SAEs) and other significant AEs will be based on GSK Core Data Standards.

Summary tables will include the number of participants with the AE, the percentage of participants with the AE. The following AE categories will be provided:

- AE
 - Any AEs
 - Common* non-serious AEs
 - AEs related to study intervention
 - AEs leading to permanent discontinuation of study intervention
- SAE
 - Any SAEs
 - SAEs related to study intervention
 - Fatal SAEs

*For disclosure purposes, common is defined as AEs occurring in at least 5% of any treatment arm. Due to the small sample size of this study this table will include all non-serious AEs.

A summary of number and percentage of participants with any adverse events by maximum intensity will be produced. The AE summaries will be sorted by System Organ Class (SOC) and Preferred term (PT) in descending order. The summary will use the following algorithms for counting the participant:

- **Preferred term row:** Participants experiencing the same AE preferred term several times with different severities will only be counted once with the maximum severity.
- **Any event row:** Each participant with at least one adverse event will be counted only once at the maximum severity no matter how many events they have.

A study intervention-related AE is defined as an AE for which the investigator classifies the possible relationship to study intervention as “Yes”. Similarly, a study intervention-related SAE is defined as an SAE for which the investigator classifies the relationship to study intervention as “Yes”. A worst-case scenario approach will be taken to handle missing relatedness data, i.e. the summary table will include events with the relationship to study intervention as ‘Yes’ or missing.

Adverse events will be coded using the standard Medical Dictionary for Regulatory Affairs (MedDRA dictionary).

Summaries tables may be omitted if the number of events is sufficiently low.

5.4.2.1. Adverse Events of Special Interest

There are no adverse events of special interest identified for this study.

5.4.3. Laboratory Data

Separate summary tables for haematology and chemistry laboratory tests as well as urine concentration parameters will be produced. Liver function laboratory tests and lipid tests will be included with chemistry lab tests. Change from baseline in laboratory parameters will be presented for continuous variables, with a summary of baseline values included in the tables.

Shift tables of worst-case results post-baseline relative to baseline will be provided for the following tests:

- For lab tests with associated Potential Clinical Importance (PCI) criteria (criteria are listed in the OPS)
- For categorical urinalysis parameters

Only post-baseline data will be included in these tables. If a participant moves to both a low and a high clinical concern range during the treatment period, then the participant is counted in both categories.

Summaries of hepatobiliary laboratory events including possible Hy's law cases will be provided in addition to what has been described above. Possible Hy's law cases are defined as any elevated alanine aminotransferase (ALT) $\geq 3 \times$ upper limit of normal (ULN) and total bilirubin $\geq 2 \times$ ULN ($> 35\%$ direct bilirubin) or ALT $\geq 3 \times$ ULN and international normalized ratio (INR) > 1.5 . Total bilirubin $\geq 2 \times$ ULN can be within 28 days following the ALT elevation and if direct bilirubin is available on the same day, it must be $\geq 35\%$ of total bilirubin. The summary will be produced for worst-case post-baseline only.

An e-DISH plot of maximum post-baseline total bilirubin versus maximum post-baseline ALT will be created.

5.4.4. Vitals Signs

A summary of change from baseline vital sign values will be provided by visit and treatment group, including systolic blood pressure, diastolic blood pressure, heart rate, respiratory rate, weight, BMI and temperature.

Blood pressure and heart rate values will be categorized into clinical concern ranges (listed in the OPS).

5.4.5. ECG

For all ECG analyses, baseline is taken to be the mean of the triplicated values collected pre-dose Day 1. The following summaries will be provided by visit:

- Summary of ECG findings (the clinical significance and interpretation of each planned ECG). In the case of triplicate ECG measurements, results will be presented separately by measurement number.
- Summary of change from baseline in ECG values. In the case of triplicate ECG measurements, summaries will use the average of the triplicate, listings will present all individual measurements.

The clinical concern ranges for ECG parameters are defined in the OPS. The absolute and change from baseline ECG values will be rounded to the nearest integer before being categorized according to the clinical concern ranges.

The following summaries of participants

- A summary of QTcF absolute values will display the number and percentage of participants with a post-baseline increase to a value within each clinical concern range for the worst-case post-baseline only.
- A summary of change from baseline QTcF values will display the number and percentage of participants with a change within each range for the worst-case post-baseline. Participants with missing baseline values will be excluded from this summary.

5.4.6. C-SSRS

A summary of C-SSRS data may be produced if there are multiple cases (>3) of suicidal ideation or behaviour, otherwise the data will be listed only.

5.5. Pharmacokinetic

Pharmacokinetic analyses will be conducted using the PK population.

Pharmacokinetic blood samples will be collected pre-dose at Week 2 (Day 15), 4 (Day 29), 8 (Day 57) and 12 (Day 85) visits to measure trough plasma concentrations of GSK2982772. Skin biopsies will be taken pre-dose at Week 4 (Day 29) and Week 12 (Day 85) to measure trough concentrations of GSK2982772 in the skin.

Summaries of trough plasma and skin GSK2982772 concentrations by visit will be produced as well as for PK predicted target engagement (the formula for this derivation is provided in the OPS).

Line plots of individual participant trough plasma and skin concentrations by visit will be produced as well as a plot for the treatment group average by visit.

Scatter plot of trough skin concentration versus trough plasma concentration at Week 4 (Day 29) and Week 12 (Day 85) will be produced.

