- 2. For women of child-bearing potential only: Serum pregnancy test must be performed at Screening. At all other visits other than Week 2, a urine pregnancy test will be performed.

 If a urine test result is positive or ambiguous, a confirmatory serum test must be performed.
- 3. Perform pre-dose during treatment period (NB excludes Week 12/Day 85 visit as Day 84 is the last day of dosing).
- 4. Triplicate ECGs will be taken at Screening and on Day 1 (Baseline). At all other specified time points single ECGs are acceptable. However, if QTc prolongation is detected triplicate ECGs should be performed. Fridericia's formula (QTcF) must be used for the QTc correction.
- 5. Blood pressure (systolic and diastolic), heart rate, respiratory rate and temperature to be assessed at all time points, as well as COVID-19 symptoms check.
- 6. Urinalysis not required on Days 29 and 57.
- 7. Blood samples will be taken after overnight fast for fasting lipid, glucose and insulin analysis.
- 8. Following Day 1, participants will take study medication at home. At the Week 2, 4, and 8 visits, the dose should not be taken before the clinic visit. Instead, the dose should be taken either on site, after all pre-dose study assessments have been completed (preferred), or after the visit (at home) if the timing of the on-site dosing would result in the dose being less than 20 hours after the last dose (i.e. overdose). There is no dose administered at Week 12/Day 85.
- 9. PGx sample collected at Day 1, after randomization and if the participant provides additional, optional informed consent. If sample is not collected at Day 1, it can be collected at any time post-randomization.
- 10. Mandatory skin biopsy samples will be collected from all participants: one non-lesional and one lesional biopsy will be collected on Day 1 (Baseline) before 1st dose of study medication. One additional lesional biopsy sample from the same plaque will be collected pre-dose at Week 12/Day 85.
- 11. One optional lesional skin biopsy sample will also be collected at Week 4/Day 29 from consenting participants only. A separate consent must be obtained.

- 12. Collection of 1 lesional skin biopsy sample required at Early Withdrawal visit if study withdrawal occurs prior to Week 12 and if the participant has completed at least 14 days of treatment. If biopsy has already been obtained within the last 14 days, then another biopsy will not be collected.

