4. STUDY DESIGN

4.1. Overall Design

This is a multicentre, randomised, double-blind (sponsor-unblinded), placebo-controlled, repeat dose study to investigate the efficacy, safety and tolerability, PK and PD and of GSK2982772 960 mg MR QD in participants with active plaque-type moderate to severe psoriasis.

Each participant will participate in the study for no more than 21 weeks. This includes a Screening period up to 35 days, an 84 day (12 week) treatment period, and a 28 day follow-up period after the last dose.

Participants will attend the clinical site to be consented and, if eligible for the study, Screening assessments will be completed. Participants who have completed Screening assessments and are eligible will be randomized in a 2:1 ratio (active to placebo) to one of the following treatments and be dosed (Day 1) within 35 days of the Screening visit:

• 960 mg GSK2982772 QD

Placebo QD

Punch skin biopsies will be performed on all participants: 1 non-lesional and 1 lesional biopsys will be collected at Baseline (predose). At Week 12 (D85), 1 lesional biopsy from the same plaque will be collected at . An additional, optional lesional biopsy may also be collected at Week 4 (D29).

An interim analysis is planned to occur when at least six participants on GSK2982772 have completed the Week 12 visit or discontinued study treatment to aid internal decision making around subsequent GSK2982772 trials. The study may be stopped for futility if the probability of a positive outcome at the end of the trial is low based on the data available at the interim. The data will be reviewed by an internal Data Review Committee. The details of the planned analyses, data to be reviewed, Data Review Committee (DRC) membership and results dissemination will be given in an interim analysis charter.

The Post-Treatment Period is 28 days (4 weeks) long.

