5.1. Inclusion Criteria

Participants are eligible to be included in the study only if all of the following criteria apply:

Age

1. Between 18 and 75 years of age inclusive, at the time of signing the informed consent.

Type of Participant and Disease Characteristics

- 2. Diagnosis of plaque psoriasis for at least 6 months before Screening visit.
- 3. Evidence of moderate to severe psoriasis, at Screening and Baseline before the first dose of study treatment, with:
 - o PASI score ≥12, AND
 - o Psoriasis plaques involving BSA ≥10%, AND
 - \circ sIGA >3
- 4. Candidate for systemic therapy or phototherapy (includes naïve or previously treated), in the opinion of the Investigator.
- 5. Agrees to avoid any prolonged exposure to natural or artificial sources of ultraviolet (UV) radiation (e.g. sunlight, tanning beds or phototherapy) from 28 days before Day 1 until the follow-up visit, which may potentially impact the participant's psoriasis in the opinion of the Investigator (see Section 5.3.3).

Weight

6. Body mass index (BMI) within the range of 18.5 to 40.0 kg/m² (inclusive).

Sex

7. Male and Female participants:

Preclinical data has not identified risk of clinically relevant genotoxicity, however there is demonstrated/suspected risk of teratogenicity/fetotoxicity. Accordingly, the following contraceptive advice must be adhered to for male and female participants.

Contraceptive use by men or women should be consistent with local regulations regarding the methods of contraception for those participating in clinical studies.

a. Male Participants:

Male participants are eligible to participate if they agree to the following during the intervention period and for at least 2 days (i.e. 5 terminal half-lives of GSK2982772) after the last dose of study intervention:

• Refrain from donating sperm

Plus either:

• Be abstinent from heterosexual intercourse as their preferred and usual lifestyle (abstinent on a long term and persistent basis) and agree to remain abstinent

OR

Must agree to use contraception/barrier as detailed below

 Agree to use a male condom and will also be advised of the benefit for a female partner to use a highly effective method of contraception as a condom may break or leak when having sexual intercourse with a woman of childbearing potential (WOCBP) who is not currently pregnant

b. Female Participants:

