1.2. Objectives, Endpoints and Estimands

1.2.1. Objectives and Endpoints

Objectives	Endpoints
Primary	

 To determine the efficacy of GSK2982772 960 mg modified release (MR) once daily (QD) for 12 weeks, compared with placebo in participants with moderate to severe plaque psoriasis. 	
 PASI75 response (achieving $\geq 75\%$ improvement from Baseline in PASI score) at Week 12.
Secondary	

 To further evaluate the efficacy of GSK2982772 960 mg MR QD for 12 weeks, compared with placebo in participants with moderate to severe plaque psoriasis. 	
Further PASI parameters:
 
 PASI50, PASI90 and PASI100 response (achieving $\geq 50\%$, $\geq 90\%$ and 100% improvement from Baseline in PASI score, respectively) at Week 12. Change from Baseline PASI scores at Week 12. Static Investigator's Global Assessment (sIGA): sIGA response (achieving a sIGA score of CCI (0) or CCI (1)) at Week 12. 
Psoriasis Body Surface Area (BSA):
 
 Change from Baseline in psoriatic BSA at Week 12.
Safety	

 To evaluate the safety and tolerability of GSK2982772 960 mg MR QD for 12 weeks, compared with placebo in participants with moderate to severe plaque psoriasis. 	
 Adverse events Clinical laboratory values (clinical chemistry, haematology and urinalysis) Vital sign measurements (blood pressure, heart rate, respiratory rate and body temperature) 12-Lead electrocardiogram (ECG) monitoring Columbia Suicide Severity Rating Scale (C-SSRS)
Pharmacokinetics	

 To assess trough plasma concentrations of GSK2982772 960 mg MR QD for 12 weeks, in participants with moderate to severe plaque psoriasis. 	
 Trough plasma concentrations of GSK2982772 at Weeks 2, 4, 8, 12.
Exploratory	

 To investigate the efficacy of GSK2982772, 960 mg MR QD over time. 	Additional PASI parameters:

Objectives	Endpoints

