1.3. Study Design

Overview of Study Design and Key Features	
Design Features	
 Phase 1b/2a, multicentre, randomised, double-blind, placebo-controlled, parallel, repeat dose study of GSK2982772 in participants with active plaque-type moderate to severe psoriasis. The maximum total duration for each participant in the study will be 21 weeks: 
 Screening period of up to 35 days Treatment period of 12 weeks (84 days) Follow-up period for up to 28 days after last dose
Study intervention	
 Participants will receive either GSK2982772 960mg MR QD or placebo for 12 weeks (84 days). No dose modifications or adjustments are permitted per protocol.
Study intervention Assignment	
 Participants will be randomised to receive either GSK2982772 or placebo in a 2:1 ratio. Randomisation will be stratified by prior biologic use.
Interim Analysis	
 One interim analysis is planned to occur when at least six GSK2982772 participants complete the Week 12 visit or withdraw from study treatment.

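### A Week 12 PK sample from a permitted Day 86-88 visit is nominally 48-96 h after the last dose, but SAP 5.5 treats it as a pre-dose trough

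*SAP*

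**What the plan says.** Dosing is of fixed length. Protocol 4.1 gives "an 84 day (12 week) treatment period", and SAP 1.3 agrees: "Participants will receive either GSK2982772 960mg MR QD or placebo for 12 weeks (84 days". In the protocol's Schedule of Activities (section 1.3), footnote 3, which is attached to the PK blood sample, reads "Perform pre-dose during treatment period (NB excludes Week 12/Day 85 visit as Day 84 is the last day of dosing". Footnote 8 adds "There is no dose administered at Week 12/Day 85". The same schedule gives the Week 12 visit, nominally Day 85, a window of plus or minus 3 days.

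The PK endpoint in SAP 1.2.1 is "Trough plasma concentrations of GSK2982772 at Weeks 2, 4, 8, 12". SAP 5.5 describes the sampling for it in these words: "Pharmacokinetic blood samples will be collected pre-dose at Week 2 (Day 15), 4 (Day 29), 8 (Day 57) and 12 (Day 85) visits". It then calls for trough summaries by visit, individual and group-average trough plots, and summaries of PK-predicted target engagement. SAP 5.8 brings the SAP 5.5 summaries into the interim package. Protocol 8.5.1 also says that PK samples precede dosing, and that the actual date and time of each sample is recorded.

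**The concern.** At Weeks 2, 4 and 8 a visit up to three days late does no harm: daily dosing continues, so a pre-dose sample is still about one dosing interval after the previous dose. Week 12 is different because dosing has a fixed end. Each day the visit slips past Day 85 adds a drug-free day, and the sample then measures washout.

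If SAP 5.5 is followed as written, such a value enters the summary of a stated endpoint under the name of trough. Week 12 could then look like falling exposure when only the visit was late. Trough is the exposure measure behind the dose rationale in protocol 4.3, and SAP 5.5.1 plots it against target engagement and may relate it to PASI score, so the label matters beyond one table.

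**Working it through.** **Inputs**
- Last dose on Day 84, none on Day 85: Schedule of Activities, footnotes 3 and 8.
- Week 12 window of plus or minus 3 days: Schedule of Activities, Treatment Period table.
- Once-daily dosing at about the same time each day: protocol 6.2. Nominal interval 24 h.
- Half-life: protocol 5.1 gives the contraception interval as "at least 2 days (i.e. 5 terminal half-lives of GSK2982772", so 48 h / 5 = 9.6 h. This is inferred; it is not a stated parameter of the modified-release tablet. Assumed range for sensitivity: 6 to 16 h.
- 14 active participants: the 14:7 split in SAP Table 2.

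**1. Reproduce the nominal schedule.** Day = 7 × week + 1 gives Days 15, 29, 57 and 85, as in the plan. Hours since the last dose on Day 85 = 24 × (85 − 84) = 24. A sample on the nominal day is a true 24 h trough.

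**2. Apply the window.** 85 ± 3 gives Days 82 to 88. On Days 82-84 dosing is still under way and a pre-dose sample is nominally 24 h after the previous dose. For later visits, hours = 24 × (visit day − 84): Day 86 gives 48 h, Day 87 gives 72 h, Day 88 gives 96 h.

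**3. Concentration relative to the 24 h trough.** Fraction = 0.5^((t − 24) / half-life), assuming mono-exponential decline after 24 h.

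| Visit | Hours since dose | Half-life 6 h | 9.6 h | 16 h |
|---|---|---|---|---|
| Day 86 | 48 | 6% | 18% | 35% |
| Day 87 | 72 | 0.4% | 3% | 12.5% |
| Day 88 | 96 | 0.02% | 0.6% | 4.4% |

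**4. Effect of one late sample on the Week 12 mean (illustration).** Assume all other values are equal and the late value is quantifiable. The geometric mean is multiplied by fraction^(1/n). At 9.6 h with n = 14 the factors are 0.177^(1/14) = 0.88 for Day 86, 0.031^(1/14) = 0.78 for Day 87 and 0.0055^(1/14) = 0.69 for Day 88. The arithmetic mean for Day 86 is multiplied by 1 − (1 − 0.177)/14 = 0.94. If only six Week 12 samples contributed at the interim (an assumption based on its trigger of at least six active participants), the geometric-mean factors would be 0.75, 0.56 and 0.42.

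**5. Look for a rule that would exclude these values.** The 20-hour limit in footnote 8 and protocol 8.4 concerns dosing and overdose, not sampling. The PK population in SAP 4 needs only one non-missing value and counts non-quantifiable results as non-missing, so it filters nothing. No other time-since-dose condition appears in either document.

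**The case against.** The strongest reply is that the rule may sit elsewhere. SAP 1 leaves data handling conventions to the OPS, and protocol 8.5.1 leaves sample collection details to the SRM. Neither is available here, so a reader who infers that the trial has no rule at all goes further than the documents allow. What stands is that SAP 5.5 itself describes every Week 12 sample as a pre-dose trough, cites no such rule, and does not fit the schedule for Days 86-88.

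The size is also open to challenge, and rightly. The half-life comes from a contraception interval. Protocol 8.4 expects monitoring after an overdose until the drug is undetectable, for at least 2 days, so some samples at 48 h or later may be non-quantifiable; the factors in step 4 would then not apply. How often visits will run late is not stated.

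Three stronger readings are tempting and fail:
- **No Week 12 sample is a trough because no dose follows it.** Step 1 shows that Day 85 is a 24 h trough. There the pre-dose label is only inexact.
- **Early visits on Days 82-84 give post-dose samples.** Footnote 8 holds the dose back only in these words: "At the Week 2, 4, and 8 visits, the dose should not be taken before the clinic visit". But the synopsis and protocol 6.2 place dosing after the pre-dose assessments, and protocol 8.5.1 places PK sampling before dosing. What remains is a wording mismatch.
- **The efficacy result or the futility decision is compromised.** Protocol 9.4.2.1 makes PK descriptive, and the decision criteria listed in SAP Table 2 concern PASI75. Individual line plots and medians would also help to expose a single late value.

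**Conclusion.** The concern holds, as a minor point. Visits on Days 86-88 are permitted, their samples are nominally 48, 72 or 96 h after the last dose, and SAP 5.5 as written counts them as troughs. At the inferred 9.6 h half-life they would be about 18%, 3% or 0.6% of the true 24 h trough, or possibly non-quantifiable. The calendar result rests on dosing stopping on Day 84 and on dose and sample falling at the same clock time. The percentages rest on an inferred half-life and simple exponential decline, and are illustrative only. The effect on PK-predicted target engagement cannot be computed because its formula is in the OPS. The consequence is confined to descriptive Week 12 PK, at the end of the study and at the interim, and to plots that use it. PASI75 and the Week 2, 4 and 8 troughs are not affected by the end of dosing.

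**What to change.** In SAP 5.5, define an evaluable trough in the same way at all four visits: drawn before any dose that day, with actual time since dose (sample time minus last recorded dose time) inside a pre-specified window around 24 h that has both a lower and an upper limit. As an example, 20-28 h would hold values at a 9.6 h half-life to between 2^(4/9.6) = 1.33 and 2^(−4/9.6) = 0.75 times the 24 h value. The pharmacokineticist should set the limits before the first unblinded look. This is an analysis window only; it changes neither dosing nor visits.

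The rule needs hours, not calendar days. A requirement that the last dose was taken the day before would admit a 20:00 dose with a 09:00 visit: 13 h, or about 2^(11/9.6) = 2.2 times the 24 h value. Footnote 8 itself anticipates visits less than 20 h after the last dose.

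Exclude values outside the window from trough summaries, trough plots and PK-predicted target engagement. List them with actual time since dose, and label them that way in the SAP 5.5.1 plots. If the OPS or SRM already holds such a rule, cite it in SAP 5.5. Reconcile the Week 12 pre-dose wording in SAP 5.5 and protocol 8.5.1 with Schedule of Activities footnotes 3 and 8.

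The cost is some SAP wording and one derivation. Sample times are already recorded (protocol 8.5.1). Home dose times are on diary cards (protocol 6.2) and must be made available for the derivation. Some values, early as well as late, will leave the trough summary, which matters a little in a trial this small; none is lost from the listings.
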